6.2.1. Obtain Written Informed Consent

All subjects must personally sign and date the institutional review board / independent ethics committee (IRB/IEC) approved informed consent form before any study procedures are performed (Section 9.1.3)

6.2.2. Recording Medical History

A complete medical, surgical and smoking history will be obtained prior to enrollment.

6.2.3. Medication History

A history of smoking and medications taken within 30 days prior to screening and during the screening period will be obtained prior to enrollment.

6.2.4. Physical Examination

A complete physical examination will be performed at the screening visit and a modified exam at all other study visits. Physical examination will be performed to monitor for any changes and will include vital signs, weight and height. Weight should be collected with the subject standing without shoes. Physical examination findings during the screening period will be reported as medical history.

6.2.5. Vital Signs

Vital signs will include pulse, respiratory rate, systolic and diastolic blood pressure, oxygen saturation level, and body temperature. They should be collected per institutional guidelines.

6.2.6. Laboratory Assessments

All samples collected in this study for laboratory assessments will be sent to the central laboratory with the exception of urine pregnancy test which will be completed at the site. Screening laboratory samples should be obtained within 7 days prior to the first dose of study drug. If the samples were obtained more than 7 days prior to first dose of study drug, only the hematology and chemistry lab samples must be repeated. Local laboratory results may be used for eligibility evaluation while pending central laboratory results.

The central laboratory will be responsible for chemistry, CBC, coagulation, urinalysis, and serum pregnancy testing per Table 6-1. Any samples collected per the Study Procedure Table (Appendix 2) may be analyzed for any tests necessary to ensure subject safety. Specific instructions for processing, labeling, and shipping samples will be provided in a central laboratory manual. The date and time of sample collection will be reported to the central laboratory.

Serum Chemistry	Hematology	Other
Sodium Potassium Chloride Lipase Amylase Bicarbonate Creatinine BUN Phosphorus LDH ^a Uric acid ^a Magnesium ^a Total bilirubin Indirect Bilirubin Direct Bilirubin ALT AST Alkaline phosphatase CPK ^b	Hemoglobin Hematocrit Red Blood Cell (RBC) count White Blood Cell (WBC) Count Neutrophils Lymphocytes Monocytes Eosinophils Basophils Platelets Urinalysis Coagulation Prothrombin Time APTT INR	 Pharmacokinetic Sampling Biomarker Sampling Syk and relevant down-stream signaling pathways mechanisms of resistance PBMC Bone Marrow Aspirate Bone Marrow Biopsy
Pregnancy Testing	Virology	
Serum Qualitative β-HCG or FSH ^a Urine pregnancy test	Hep B Hep C HIV	

Table 6-1.	Analytes
------------	----------

a Screening only

b At Screening, Day 1 of each cycle and End of Treatment

6.2.7. Bone Marrow Aspirate and Biopsy

Bone marrow aspirate/biopsy samples will be assessed by a local hematopathologist. Unstained slides should be made available to the sponsor for central review. Results from assessment of bone marrow aspirate/biopsy samples obtained as part of the subject's routine medical care may be used if the documentation is available.

6.2.8. Eastern Cooperative Oncology (ECOG) Performance Status

The ECOG performance status is an investigator assessment of the impact of the disease on the subject's activities of daily living. It is assessed on a 6-point scale as described in Appendix 6 {Oken 1982}.

6.3. Biomarker Testing

6.3.1. Biomarker Samples to Address the Study Objectives:

The following biological specimens will be collected in this study and will be used to evaluate the association of exploratory systemic and/or tissue specific biomarkers with study drug response including efficacy and/or adverse events, as well as to increase knowledge and understanding of the biology of related diseases. The specific analyses will include, but will not be limited to, the biomarkers and assays listed below. Because biomarker science is a rapidly evolving area of investigation, and adverse events in particular are difficult to predict, it is not possible to specify prospectively all tests that will be done on the specimens provided. The testing outlined below is based upon the current state of scientific knowledge. It may be modified during or after the end of the study to remove tests no longer indicated and/or to add new tests based upon the growing state of the art knowledge. Specimens will be collected from all subjects which may allow for individualized drug therapy for subjects in the future. Blood samples will be collected from all subjects at baseline and after treatment to assess changes in the Syk pathway, relevant downstream pathways and Syk associated pathways in blasts. The testing may include assessing phosphorylation of Syk and other downstream mediators, cytokines and chemokines. Specimens will be collected from all subjects. **PPD**

Blood and bone marrow samples will be collected to study:

- Mechanisms of resistance to GS-9973 by analysis of DNA and genes, and/or proteins that change between baseline and at disease progression. These studies will allow us to identify new and improved therapies for ALL
- Effects of GS-9973 on signaling and minimal residual disease to better understand the effects of GS-9973 on disease burden

6.3.2. Biomarker Samples for Optional Future Research

6.4. Pretreatment Assessments

6.4.1. Screening Visit

Subjects will be screened within 28 days of their first administration of study treatment to determine eligibility for participation in the study. The following will be performed and documented at screening:

- Obtain written informed consent
- Obtain medical history
- Obtain smoking status
- Complete physical examination including, vital signs, body weight, and height
- Obtain blood samples
- Bone marrow aspirate/biopsy (if not done within 28 days of the first dose of GS-9973)
- CT scan or PET-CT of affected site/s for subjects with EMD only and without measureable BM involvement
- Record any serious adverse events and all adverse events related to protocol mandated procedures occurring after signing of the consent form

Subjects meeting all of the inclusion criteria and none of the exclusion criteria will return to the clinic within 28 days of screening for enrollment into the study.

From the time of obtaining informed consent through the first administration of study drug (GS-9973), record all serious adverse events (SAEs), as well as any adverse events related to protocol-mandated procedures on the adverse events case report form (CRF/eCRF). All other untoward medical occurrences observed during the screening period, including exacerbation or changes in medical history are to be captured on the medical history CRF/eCRF. See Section 7.6 Adverse Events and Toxicity Management for additional details.

6.5. Treatment Assessments

Subjects who have met all eligibility criteria will come to the clinic to start the Lead-in phase of the study and to perform study required procedures prior to dosing. Review prior/ concomitant medications and record adverse events at each clinic visit.

For study purposes, the GS-9973 Lead-in is 7 days.

6.5.1. Lead-in Phase:

• Review prior/concomitant medication

- Record any adverse events
- Vital signs; including blood pressure, respiratory rate, pulse, temperature, oxygen saturation
- Performance status (ECOG)
- Modified physical exam including weight
- Smoking Status
- Laboratory assessments (Section 6.2.6):
 - Hematology
 - Chemistry
 - Coagulation
 - Pharmacokinetic sampling at pre-dose and 1.5 hours post-dose of GS-9973 (± 30 minutes)
 - Biomarker sampling (pre-dose)
 - Urine pregnancy test for females of child bearing potential
- Study drug dispensation

6.5.2. Cycle 1

After completing the 7 day Lead-in phase, the subjects will start Cycle 1 for 28 days.

6.5.2.1. Cycle 1: Day 1

- Review prior/concomitant medication
- Record any adverse events
- Obtain smoking status
- Vital signs; including blood pressure, respiratory rate, pulse, temperature, oxygen saturation level
- Performance status (ECOG)
- Modified physical exam including weight
- Laboratory assessments (Section 6.2.6.):
 - Hematology
 - Chemistry
- CONFIDENTIAL

- Coagulation
- Pharmacokinetic peripheral blood sampling at pre-dose and 1.5 hours post-dose of GS-9973 (± 30 minutes)
- Biomarker sampling
- PPD

• Study drug dispensation

- VCR administration
- Urine pregnancy test for females of child bearing potential

6.5.2.2. Cycle 1: Day 8

- Review prior/concomitant medication
- Record any adverse events
- Vital signs; including blood pressure, respiratory rate, pulse, temperature, oxygen saturation level
- Performance status (ECOG)
- Modified physical exam
- Laboratory assessments (Section 6.2.6.):
 - Hematology
 - Chemistry
 - Coagulation
 - Pharmacokinetic peripheral blood sampling pre-dose and 1.5 hours post-dose of GS-9973 (± 30 minutes)
 - Biomarker sampling (pre-dose)
- VCR administration
- Dexamethasone dispensation
- Bone marrow aspirate/biopsy
- CT scan or PET-CT of affected site/s for subjects with EMD only and without measureable BM involvement (Patients with no BM involvement and only EMD will not require BM aspirate/biopsy on cycle 1 day 8).

6.5.2.3. Cycle 1: Day 15

- Review prior/concomitant medication
- Record any adverse events
- Vital signs; including blood pressure, respiratory rate, pulse, temperature, oxygen saturation level
- Performance status (ECOG)
- Modified physical exam
- Laboratory assessments (Section 6.2.6.):
 - Hematology
 - Chemistry
 - Coagulation
- VCR administration
- 6.5.2.4. Cycle 1: Day 22
- Review prior/concomitant medication
- Record any adverse events
- Vital signs; including blood pressure, respiratory rate, pulse, temperature, oxygen saturation level
- Performance status (ECOG)
- Modified physical exam
- Laboratory assessments (Section 6.2.6.):
 - Hematology
 - Chemistry
 - Coagulation
- VCR administration
- Dexamethasone dispensation
- 6.5.2.5. Cycle 1: Day 28
- Review prior/concomitant medication

- Record any adverse events
- Vital signs; including blood pressure, respiratory rate, pulse, temperature, oxygen saturation level
- Performance status (ECOG)
- Modified physical exam including weight
- Laboratory assessments:
 - Hematology
 - Chemistry
 - Pharmacokinetic peripheral blood sampling at pre-dose and 1.5 hours post-dose of GS-9973 (± 30 minutes)
 - Biomarker sampling (pre-dose)
- CNS Prophylaxis (per institutional standard)
- Bone marrow aspirate/biopsy
- Cerebrospinal fluid (CSF) for PK analysis (prior to CNS prophylaxis administration)
- CT scan or PET-CT of affected site/s for subjects with EMD only and without measureable BM involvement (Patients with no BM involvement and only EMD will not require BM aspirate/biopsy on cycle 1 day 28)
- Study drug dispensation; if needed for cycle break coverage

6.5.3. Cycle 2

Subjects may continue to Cycle 2 within 7 days of completing Cycle 1.

6.5.3.1. Cycle 2: Day 1

- Review prior/concomitant medication
- Record any adverse events
- Obtain smoking status
- Vital signs; including blood pressure, respiratory rate, pulse, temperature, oxygen saturation level
- Performance status (ECOG)

CONFIDENTIAL

- Modified physical exam including weight
- Laboratory assessments (Section 6.2.6.):
 - Hematology
 - Chemistry
 - Coagulation
- Urine pregnancy test for females of child bearing potential
- Study drug dispensation
- VCR administration
- Dexamethasone dispensation
- 6.5.3.2. Cycle 2: Day 8
- Review prior/concomitant medication
- Record any adverse events
- Vital signs; including blood pressure, respiratory rate, pulse, temperature, oxygen saturation level
- Performance status (ECOG)
- Modified physical exam
- Laboratory assessments (Section 6.2.6.):
 - Hematology
 - Chemistry
 - Coagulation
- VCR administration
- 6.5.3.3. Cycle 2: Day 15
- Review prior/concomitant medication
- Record any adverse events

- Vital signs; including blood pressure, respiratory rate, pulse, temperature, oxygen saturation level
- Performance status (ECOG)
- Modified physical exam
- Laboratory assessments (Section 6.2.6.):
 - Hematology
 - Chemistry
 - Coagulation
- VCR administration
- Dexamethasone dispensation
- 6.5.3.4. Cycle 2: Day 22
- Review prior/concomitant medication
- Record any adverse events
- Vital signs; including blood pressure, respiratory rate, pulse, temperature, oxygen saturation level
- Performance status (ECOG)
- Modified physical exam
- Laboratory assessments (Section 6.2.6.):
 - Hematology
 - Chemistry
 - Coagulation
- VCR administration
- 6.5.3.5. Cycle 2: Day 28
- Review prior/concomitant medication
- Record any adverse events

- Vital signs; including blood pressure, respiratory rate, pulse, temperature, oxygen saturation level
- Performance status (ECOG)
- Modified physical exam
- Laboratory assessments :
 - Hematology
 - Chemistry
 - Pharmacokinetic peripheral blood sampling at pre-dose and 1.5 hours post-dose of GS-9973 (± 30 minutes)
 - Biomarker sampling (pre-dose)
- Study drug dispensation, if needed for cycle break coverage
- CNS prophylaxis (per institutional standard)
- Bone marrow aspirate/biopsy
- Cerebral fluid (CSF) for PK analysis (prior to CNS prophylaxis administration)
- CT scan or PET-CT of affected site/s for subjects with EMD only and without measureable BM involvement, unless imaging was performed within 30 days of end of treatment (Patients with no BM involvement and only EMD will not require BM aspirate/biopsy on cycle 2 day 28).

6.6. Maintenance

Subjects who obtain clinical benefit in the opinion of the treating physician may continue GS-9973 at the assigned dose level during maintenance for up to 36 cycles. VCR will be administered on Day 1 of each 28-day cycle. Dexamethasone (20 mg total dose daily for 4 days, either 10 mg twice daily or 20 mg once daily) will be taken on Days 1-4 and 15-18 of each 28-day cycle.

Refer to Appendix 2 for procedures performed during maintenance. Study drug (GS-9973) will be dispensed at Day 1 of each cycle during maintenance.

Bone marrow evaluations and additional central nervous system (CNS) prophylaxis can be performed as clinically indicated per institutional standards in the maintenance.

6.7. End of Study Treatment Assessments

Subjects will be removed from study treatment when any of the criteria listed in Section 6.8 apply.

The following procedures will be conducted when a subject goes off study treatment and prior to initiating a new regimen.

If the subject chooses not to continue participation on the study, the procedures listed below are to be conducted within 14 days of the last dose of study treatment or prior to initiating a new therapy.

- Review prior/concomitant medication
- Record any adverse events
- Performance status (ECOG)
- Modified physical exam including weight
- Vital signs; including blood pressure, respiratory rate, pulse, temperature, oxygen saturation level
- Laboratory assessments (Section 6.2.6.):
 - Chemistry
 - Hematology
 - Coagulation
 - Biomarker sampling
- Obtain bone marrow aspirate/biopsy samples for disease assessment and Biomarker testing
- CT scan or PET-CT of affected site/s for subjects with EMD only and without measureable BM involvement unless imaging was performed within 30 days of end of treatment (Patients with no BM involvement and only EMD will not require BM aspirate/biopsy)

6.7.1. **30-Day Follow-up**

After the last dose of study drug, subjects should be followed for any drug-related AEs and/or ongoing serious adverse events (SAEs) until those events have resolved or become stable, whichever occurs later. The site will contact the study subject regardless of AE/SAE status approximately 30 days after the subject's last dose of study drug to assess adverse events since the last study visit and review concomitant medications. Subject should be contacted by phone (or in person, if necessary) to assess the subject's condition and record any adverse events reported during the follow-up contact. Phone call or visit should be documented.

6.7.2. Long Term Follow-Up

Long term follow-up for survival will be conducted every 3 months (\pm 4 weeks) after the discontinuation of treatment visit until end of study. Information to be gathered includes ALL treatments, other malignancies, and survival which could be collected during a routine clinic visit, other contact with the subject, or via telephone. Gilead reserves the right to discontinue or shorten the duration of participation in the long term follow-up period at any time.

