3.3.3. Maintenance

It is anticipated that most subjects will receive hematopoietic stem cell transplant (HSCT) therapy with curative intent if a complete remission (CR) is reached. In the absence of suitable alternative therapeutic options, subjects who obtain clinical benefit (at least PR) after completing both cycles of induction therapy in dose escalation may continue GS-9973 at the assigned dose level in the maintenance phase for up to 36 cycles. Subjects will continue GS-9973 and VCR at their assigned dose. GS-9973 will continue to be taken orally twice daily with VCR given on Day 1 of each 28-day cycle. Dexamethasone may be administered as a single dose of 20 mg once daily or a divided dose of 10 mg twice daily on Days 1-4 and Days 15-18 of each 28-day cycle.

Bone marrow evaluations and additional central nervous system (CNS) directed therapy can be performed as clinically indicated in the maintenance phase.

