8.5.1. Primary Analysis

Categorical Endpoints

Overall remission rate and other response rate variables will be described. In the analyses of overall remission rate at induction completion, subjects who do not have sufficient baseline or on study tumor assessment to characterize response will be counted as failures. For all analyses, the corresponding 95% exact CIs will be presented.

Time-to-Event Endpoints

RFS, EFS and OS will be analyzed using Kaplan-Meier (KM) methods. The KM estimate of the survival function will be computed and the results will be presented using KM curves. The median will be provided along with the corresponding 95% CI. Additionally, the 25% and 75% percentiles for these endpoints will also be provided. In addition, the estimated rate at 6 month, 12 month, 2 year and 3 year will be reported.

The following censoring rules will be applied:

RFS: For a subject who is not known to have relapsed or died by the end of the study follow-up or data cutoff, RFS is censored on the date of the last available disease assessment of the subject.

EFS: For subjects with none of the events defined in EFS before the end of the study follow-up or data cutoff, EFS is censored at the date of the last available disease assessment of the subject.

OS: For a subject who is not known to have died by the end of study follow-up or data cutoff, OS is censored on the date the subject is last known to be alive.

Analysis of remission duration will be analyzed using cumulative incidence by considering death without relapse as competing risks. The estimate of the cumulative incidence of relapse (CIR) will be reported with the associated 95% CI. For a subject with no report of relapse by the end of the study follow-up or data cutoff date, observation is censored on the date of the last available assessment of the subject.

Continuous Endpoints

Continuous endpoints (e.g. TTR and TTC) will be summarized using descriptive statistics.

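### Long-term follow-up does not list relapse, so the cumulative incidence of relapse planned in Protocol 8.5.1 is biased downward for responders who leave treatment, and RFS is misdated

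*Protocol*

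**What the plan says.** **Analysis.** Protocol 8.5.1 plans Kaplan-Meier RFS with estimates at 6 and 12 months and at 2 and 3 years. For subjects not known to have relapsed or died, "RFS is censored on the date of the last available disease assessment of the subject". For remission duration: "Analysis of remission duration will be analyzed using cumulative incidence by considering death without relapse as competing risks".

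**Data after treatment.** Protocol 6.7.2: "Long term follow-up for survival will be conducted every 3 months". The content is given as "Information to be gathered includes ALL treatments, other malignancies, and survival which could be collected during a routine clinic visit", with other contact or telephone also allowed. Relapse is not among the named items.

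**Who is in that follow-up.** Protocol 3.3.3 anticipates that most subjects reaching CR will go on to transplant. The synopsis limits this to those who are transplant eligible.

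**Data on treatment.** Responders without a suitable alternative "may continue GS-9973 at the assigned dose level during maintenance for up to 36 cycles" (Protocol 6.6). Marrow is not scheduled in that phase: "Bone marrow evaluations and additional central nervous system (CNS) directed therapy can be performed as clinically indicated in the maintenance phase" (Protocol 3.3.3). The procedures table (Protocol Appendix 2, SAP Appendix 1) does schedule blood counts with differential and physical examinations there. When a subject goes off treatment, before any new regimen, Protocol 6.7 requires: "Obtain bone marrow aspirate/biopsy samples for disease assessment and Biomarker testing". Subjects with extramedullary disease only have imaging instead.

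**SAP.** Section 6 covers four response rates at the end of induction. RFS, EFS and OS appear in the abbreviation list, but the visible text gives no method for RFS or CIR. The exploratory objectives are redacted.

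**The concern.** The two relapse-based analyses need an input that the follow-up schedule does not ask for. A responder who leaves for transplant has a last marrow at departure. From then on the listed data are survival, ALL treatments and other malignancies.

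Three consequences follow for such a subject:

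- **Relapse then death:** the database holds a death and no relapse. In CIR this becomes a competing death, so relapse is undercounted and death without relapse is overcounted.
- **Same subject in RFS:** the event is counted, but it is dated at death and not at the earlier relapse.
- **Alive at data cutoff:** the subject is censored at the end-of-treatment assessment, even if known to be in remission much later.

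A reader of the report would see a remission that appears more durable, and a non-relapse mortality that appears higher, than the data would show with relapse recorded.

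**Working it through.** **1. Stated figures.** The documents give no numerical target or assumption for RFS or CIR. The only relevant sample size is that for escalation: 18 / (1 - 0.10) = 20, which reproduces the stated 20.

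**2. How far the landmarks depend on off-treatment data.** Maintenance is at most 36 x 28 = 1008 days. The longest scheduled treatment, ignoring holds, is 7 (lead-in) + 28 + 7 (permitted gap) + 28 + 1008 = 1078 days, and 1078 / 365.25 = 2.95 years. The 3-year RFS rate therefore rests on off-treatment data even for a subject who completes all maintenance. For a subject who leaves for transplant after induction, all four landmarks do.

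**3. Size, under assumed rates.** The documents give no relapse or death rates, so these are assumptions chosen to show a range:

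- constant hazards of relapse (r = ln 2 / median), of death without relapse (d), and of death after relapse;
- 40,000 simulated responders per case, with follow-up uniform between 6 and 36 months;
- as written: off-treatment relapse is not recorded, deaths are known, and off-treatment survivors are censored at departure (0.03 months);
- on-treatment relapse is taken as fully detected.

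With full recording there is a closed form to check against: RFS(12) = exp(-12(r + d)) and CIR(12) = r/(r + d) x [1 - RFS(12)]. For a 6-month median and d = 0.02, r = 0.1155. RFS = exp(-1.626) = 0.20, and CIR = (0.1155/0.1355) x 0.803 = 0.68, which matches the simulation.

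Twelve-month results (CIR / death without relapse / RFS):

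| Median relapse; median relapse to death; d per month | Relapse recorded | As written, half off treatment | As written, all off treatment |
|---|---|---|---|
| 4 mo; 4 mo; 0.01 | 0.84 / 0.05 / 0.11 | 0.46 / 0.37 / 0.17 | 0.00 / 0.75 / 0.25 |
| 6 mo; 6 mo; 0.02 | 0.68 / 0.12 / 0.20 | 0.40 / 0.35 / 0.25 | 0.00 / 0.67 / 0.33 |
| 12 mo; 6 mo; 0.02 | 0.45 / 0.16 / 0.39 | 0.28 / 0.33 / 0.39 | 0.00 / 0.62 / 0.38 |

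If no responder is off treatment, nothing changes.

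**4. Reading the table.** CIR falls in every case with subjects off treatment, and the fall grows with their share. The zeros in the last column follow by construction, because no relapse is recorded. RFS changes by 0.25 - 0.11 = +0.14 at most and 0.38 - 0.39 = -0.01 at least. Late dating of events raises it, and early censoring of survivors lowers it.

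**5. Maintenance.** Relapse can be declared on blood, marrow or any extramedullary site (Protocol Appendix 4). Blood counts and examinations are scheduled, relapsed disease ends treatment (synopsis, Duration of Treatment), and the end of treatment brings a marrow. A marrow-only relapse may be found late, but it can be observed.

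**The case against.** **The analyses may no longer be live.** The SAP covers Phase 1b only, for a synoptic report, and its visible efficacy section has no RFS or CIR. This limits the weight of the point but does not remove it. Amendment 5 was written after expansion was abandoned and still contains 8.5.1. The SAP's exploratory text is redacted, and nothing visible says that the analyses are dropped.

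**Definitions are unseen.** The exploratory endpoint definitions are redacted. If RFS and remission duration were censored at transplant or new therapy, later relapse would not be needed. The visible censoring rules in 8.5.1 contain no such provision. The eCRF is also unseen and might hold a relapse field.

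**Follow-up is not closed to relapse.** The list in 6.7.2 is introduced by a non-exhaustive verb, and new ALL treatment can signal relapse. It would be too strong to say that relapse is never asked about. But transplant in remission is itself an ALL treatment, untreated relapse gives no signal, and no proxy rule is stated. Protocol 7.1.2.1 asks for unrelated progression to be captured on the eCRF, and death due to ALL would show that relapse had occurred. Neither gives a scheduled relapse date.

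**Deaths of unknown relapse status.** 8.5.1 does not say how to class them. That is correct. With a death date and no relapse record, the competing-event rule gives death without relapse by default, and the fix should settle this.

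**Stronger readings that the documents do not support.** A reader might infer that RFS misclassifies deaths after relapse. It does not, because death is an RFS event either way. A reader might infer that maintenance subjects are censored at induction. Their scheduled counts, examinations and end-of-treatment marrow contradict that. A reader might infer that CIR goes to zero whatever the truth. That needs every responder to leave at once with no relapse captured.

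**Conclusion.** The mismatch stands in a limited form. For responders who leave treatment, the written plan does not secure a relapse date, while 8.5.1 needs one. CIR is then biased downward by an amount set by the share off treatment: from 0.45-0.84 to 0.28-0.46 at 12 months if half are off, under the assumed rates. The net direction of the RFS bias is uncertain.

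This rests on assumed hazards, on no relapse being recorded off treatment, on deaths being known, and on deaths of unknown relapse status being classed as death without relapse. The practical impact is small. The endpoints are neither primary nor secondary, 20 subjects were planned for escalation, both documents cite a low response rate, and with so few responders the 2- and 3-year rates would be imprecise even with complete relapse data.

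**What to change.** - **Protocol 6.7.2 and the follow-up eCRF:** at the existing 3-monthly contact, record relapse as yes, no or unknown, with the date of relapse or the date last known relapse-free.
- **Protocol 8.5.1, and the SAP if it carries these analyses:** censor RFS and CIR at the date last known relapse-free. Present CIR both ways for deaths of unknown relapse status, once as death without relapse and once as relapse.
- **Alternative:** if RFS and CIR will not be reported, say in the protocol or SAP that they are dropped.

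The cost is a status field with its date, plus the wording changes. No visit or test is added. The downside is that relapse would be reported by contact and not centrally confirmed.
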